### **4.3 OTHER SCREENING CONSIDERATIONS**

For coronavirus disease of 2019 screening, Severe Acute Respiratory Syndrome Coronavirus 2 (SARS-CoV-2) testing will be conducted as per clinical research unit's policy at the time of conduction.

#### **4.3.1 Lifestyle Restrictions**

The following lifestyle restrictions will be followed by the participants throughout the study until EOS:

1. Participants will abstain from alcohol for 48 hours prior to study drug administration and until the last set of laboratory evaluations at EOS.
2. Participants will abstain from smoking and drug use for the duration of the study. List of drugs that will be screened at screening and check-in are provided in Section 6.2.3 (Other analyses).
3. Foods or herbal preparations, including grapefruit juice, grapefruit/grapefruit-related citrus fruits (eg, Seville oranges, pomelos), are prohibited for the duration of the study.

## **4.4 WITHDRAWAL OF PARTICIPANTS FROM THE STUDY**

### **4.4.1 Reasons for Withdrawal**

Participants can withdraw consent and discontinue from the study at any time, for any reason, without prejudice to further treatment.

The investigator may withdraw a participant from the study if the participant:

1. Is non-compliant with the protocol;
2. Experiences a SAE or intolerable AE(s) that in the investigator's opinion requires withdrawal from the study;
3. Has laboratory safety assessments that reveal clinically significant hematological or biochemical changes from baseline values;
4. Develops, during the course of the study, symptoms or conditions listed in the exclusion criteria;
5. Requires a medication prohibited by the protocol; or
6. Requests an early discontinuation for any reason.

The investigator can also withdraw a participant upon the request of the sponsor, or if the sponsor terminates the study. Upon occurrence of an SAE or intolerable AE, the investigator will confer with the sponsor. If a participant is discontinued because of an AE, the event will be followed until it is resolved, stable, or judged by the investigator to be not clinically significant.

### **4.4.2 Handling of Withdrawals**

Participants are free to withdraw from the study at any time upon request. Participant's participation in the study may be stopped at any time at the discretion of the investigator or at the request of the sponsor.

When a participant withdraws from the study, the reason(s) for withdrawal shall be recorded by the investigator on the relevant page of the eCRF. Whenever possible, any participant who withdraws from the study prematurely will undergo all EOS assessments. Any participant who fails to return for final assessments will be contacted by the site in an attempt to have them comply with the protocol. The status of participants who fail to complete final assessments will be documented in the eCRF.

### **4.4.3 Replacements**

Any participant who is withdrawn or discontinued from the study may be replaced.

## 5. STUDY TREATMENTS

### 5.1 TREATMENTS ADMINISTERED

For Part A, each participant will be randomly assigned to 1 of 6 treatment sequences; the sequences will dictate the order in which each participant receives each of the planned treatments. Refer to Section 3 for a description of the treatment sequences.

For Part A, each participant will receive the following study treatments in a crossover design:

- Treatment 1: 900 mg plixorafenib ( $6 \times 150$  mg tablets) administered after overnight fast (fasted state).
- Treatment 2: 900 mg plixorafenib ( $6 \times 150$  mg tablets) + cobicistat ( $1 \times 150$  mg tablet) administered after overnight fast (fasted state).
- Treatment 3: 900 mg plixorafenib ( $6 \times 150$  mg tablets) + cobicistat ( $1 \times 150$  mg tablet) administered following a high fat, high caloric meal (fed state).

For Part B, each participant will be randomly assigned to 1 of 4 treatment sequences; the sequences will dictate the order in which each participant receives each of the planned treatments. Refer to Section 3 for a description of the treatment sequences.

For Part B, each participant will receive three of the following study treatments per randomization in a crossover design:

- Treatment A: 900 mg plixorafenib ( $6 \times 150$  mg tablets) administered after overnight fast (fasted state).
- Treatment B: 900 mg plixorafenib ( $6 \times 150$  mg tablets) administered following a high fat, high caloric meal (fed state-high fat meal).
- Treatment C: 900 mg plixorafenib ( $6 \times 150$  mg tablets) administered following a low-fat meal (fed state-low-fat meal).
- Treatment D: 900 mg plixorafenib ( $6 \times 150$  mg tablets) administered with 150 mg cobicistat ( $1 \times 150$  mg tablet) following a low-fat meal (fed state-low-fat meal).

There will be a washout of at least 7 days between dosing in each treatment period.

### 5.2 STUDY DRUGS

The study drugs that will be used are as follows:

Product	Supplied Formulation
Plixorafenib	150 mg tablet
Cobicistat	150 mg tablet

Plixorafenib is available as white to off-white oval tablet (uncoated or film-coated tablets) and contains the following inactive excipients: HPMCAS, sodium lauryl sulfate, microcrystalline cellulose, mannitol, croscarmellose sodium, silicon dioxide, and sodium stearyl fumarate. Film-coated tablets also contain titanium dioxide, polyvinyl alcohol, macrogol, and talc.

Further information on the study drug can be found in the Investigator's Brochure (Fore Biotherapeutics 2023).

Cobicistat (150 mg) tablet is commercially available and will be supplied or obtained by the clinical unit according to the study agreement and in accordance with local guidelines. Refer to the prescribing of cobicistat for more details on the formulation, preparation, storage conditions, the approved indications, known precautions, warnings, and adverse reactions. Cobicistat will be dispensed by the pharmacy staff at the clinical study site.

### **5.2.1 Study Drug Packaging and Storage**

Fore Biotherapeutics will provide the investigator and clinical unit with adequate quantities of plixorafenib. Cobicistat will be provided by clinical unit. Detailed instructions for the preparation of study treatments will be provided in a separate pharmacy manual.

All study drugs must be stored according to the labeled instructions in a secure cabinet or room with access restricted to necessary clinic personnel. A temperature log to record compliance with storage conditions will be required to be maintained at the site.

Instructions regarding storage and handling of plixorafenib is provided in the pharmacy manual.

### **5.2.2 Study Drug Accountability**

The investigator will maintain accurate records of receipt of all study drugs, including dates of receipt. Accurate records will be kept regarding when and how much study drug is dispensed and used by each participant in the study. Reasons for departure from the expected dispensing regimen must also be recorded. At the completion of the study, and to satisfy regulatory requirements regarding drug accountability, all study drugs will be reconciled and retained or destroyed according to applicable regulations.

## **5.3 METHOD OF ASSIGNING PARTICIPANTS TO TREATMENT GROUPS**

The Contract Research Organization will generate the randomization schedule. Participants who meet all inclusion and none of the exclusion criteria will be randomly assigned to one of the 6 treatment sequences for Part A and one of the 4 treatment sequences for Part B as described in Section 3. Randomization numbers (in sequential order) will be assigned before the first dose of study drug is administered. There will be no stratification.

## **5.4 BLINDING**

This is an open-label study.

## **5.5 TREATMENT COMPLIANCE**

All doses of the study drug will be administered in the clinical unit under direct observation of clinic personnel and recorded in the eCRF. Clinic personnel will confirm that the participant has received the entire dose of study drug.

The date and time of study drug dosing will be recorded on the appropriate page of the eCRF. If a participant is not administered study drug, the reason for the missed dose will be recorded.

### **5.5.1 Prior and Concomitant Medications**

Prohibited and/or restricted prior and concomitant medications and therapies are provided in Sections 4.2 and 5.5.1.2.1. Prior and concomitant medications and therapies will be coded using the latest version of the World Health Organization Drug Dictionary.

#### **5.5.1.1 Prior Medications**

Information regarding prior medications taken by the participant within the 30 days before signing the ICF will be recorded in the participant's eCRF.

#### **5.5.1.2 Concomitant Medications**

During the study, any concomitant medication deemed necessary for the welfare of the participant may be given at the discretion of the investigator. If a concomitant medication is taken, except for those specified in the protocol, a joint decision will be made by the investigator and the sponsor to continue or discontinue the participant based on the time the medication was administered, its pharmacology and PK, the potential for drug interactions, and whether the use of the medication will compromise the safety of the participant or the interpretation of the data. The investigator is responsible for ensuring that details regarding the medication are adequately recorded in the eCRF.

##### **5.5.1.2.1 Prohibited Medications**

Agents that are known strong inducers or inhibitors of CYP3A4 are prohibited throughout the study. Herbal medications including St. John's Wort, are prohibited, throughout the study. Agents that are contraindicated with cobicistat are prohibited throughout the study.

## **6. STUDY PROCEDURES**

Before performing any study procedures, all potential participants will sign an ICF as outlined in Section 9.2.2.3. Participants will undergo study procedures at the time points specified in the SOE (Section 3.3).

The total amount of blood collected from each participant over the duration of the study, including any extra assessments that may be required, will not exceed 500 mL.

## 6.1 PHARMACOKINETIC AND PHARMACOGENOMICS ASSESSMENTS AND ENDPOINTS

Following administration of the study treatments, participants will have serial blood drawn (Part A and Part B) and urine (for Part A only) samples collected for determination of blood and urine concentration of plixorafenib.

Blood PK sample collection timepoints are provided in Table 6-1.

**Table 6-1 Blood PK Sampling Timepoints**

Study Days Timepoints	D1, D8, D15 (Dosing)	D2, D9, D16	D3, D10, D17	D4, D11, D18	D5, D12, D19
0 hour (0800)*	✓ (Predose)**	✓ (24 h)	✓ (48 h)	✓ (72 h)	✓ (96 h)
0.5 hour (0830)	✓				
1 hour (0900)	✓				
2 hour (1000)	✓				
3 hour (1100)	✓				
4 hour (1200)	✓				
6 hour (1400)	✓				
8 hour (1600)	✓	✓ (32 h)			
10 hour (1800)	✓				
12 hour (2000)	✓				

D, day; h, hours

\*Nominal clock time.

\*\*Predose sample will be collected within 15 minutes prior to the dosing. 0 hour means dosing of study drug.

**For Part A only:** Prior to the predose sample, each participant will be instructed as to urine collection methods. Urine samples for the determination of plixorafenib concentrations and its metabolites will be collected at selected time intervals, as specified in the table below. All participants will be asked to void their bladder within 45 minutes prior to dosing. After administration of plixorafenib, all urine will be collected completely per each collection interval. Urine portions will be pooled per participant within this collection interval. Just prior to the end of the sampling interval, participants will be encouraged to void their bladder again to complete the collection. The start and end times of the urine collection will be recorded. Three aliquot (5 mL each) will be obtained from each pooled urine sample: 1 for the quantification of plixorafenib, 1 for the metabolite analysis, and 1 as a back-up. Instructions for sample preparation and storage can be found in the study lab manual.

Urine samples for the quantitation of plixorafenib, collection timepoints are in Table 6-2.

**Table 6-2 Urine Sample Collection Timepoints**

Study Days Timepoints	D1, D8, D15 (Dosing Day)	D2, D9, D16
Predose*	✓	

Study Days Timepoints	D1, D8, D15 (Dosing Day)	D2, D9, D16
0-4 hours	✓	
4-8 hours	✓	
8-12 hours	✓	
12-24 hours		✓
24-48 hours		✓

D, days.

\*45 minutes prior to dosing.

The following PK parameters will be calculated using model-independent approaches (NCA) from plixorafenib individual plasma concentrations, whenever practical.

### Plasma Parameters (Part A and B)

- Area under the plasma concentration versus time curve (AUC) from time 0 to the last quantifiable concentration ( $AUC_{0-t}$ ).
- AUC from time 0 extrapolated to infinity ( $AUC_{0-inf}$ ).
- Maximum observed plasma concentration ( $C_{max}$ ).
- Time to maximum observed plasma concentration ( $T_{max}$ ).
- Terminal elimination rate constant ( $K_{el}$ ).
- Terminal phase half-life ( $t_{1/2}$ ).
- Apparent oral clearance ( $CL/F$ ).
- Apparent volume of distribution ( $V_d/F$ ).
- Terminal rate constant calculated from the terminal slope of the log-linear regression of concentration with time ( $\lambda_z$ ).
- Calculated lag time: time taken for the drug to appear in the systemic circulation following administration, when applicable ( $T_{lag}$ ).

### Urine Parameters (Part A Only)

- Cumulative amount of plixorafenib excreted in urine, calculated as the sum of the product of urine concentration and urine volume ( $A_e$ ).
- Percent of dose excreted in urine in 48 hours calculated as  $100 \cdot A_e / \text{Dose}$

Blood and urine samples may be used to evaluate the metabolic profile of plixorafenib and the results will be described separately.

Blood and/or plasma samples may be used to measure endogenous biomarkers, such as coproporphyrin I, to assess possible transporters inhibition.

### **6.1.1 Pharmacokinetic Sample Collection**

Details for the collection, processing, storage, and shipping of PK samples will be provided to the clinical unit separately.

### **6.1.2 Pharmacokinetic Sample Analysis**

Plasma samples for the quantitation of plixorafenib will be analyzed using a validated liquid chromatography coupled with tandem mass spectrometry assay (LC/MS/MS method) for plixorafenib in human plasma. Assay results and validation details will be provided in a separate bioanalytical report. A qualified assay will be used to quantitate plixorafenib urine concentrations. An exploratory assay will be used for metabolite identification in plasma and urine.

### **6.1.3 Pharmacogenomic Sample Analysis**

A blood sample for pharmacogenomic evaluation will be collected at screening. Possible effect of pharmacogenomic variations on the PK of plixorafenib and/or the effect of cobicistat, including but not limited to polymorphisms in P-gp, BCRP, and UGT, will be examined, if feasible.

## **6.2 SAFETY ASSESSMENTS AND ENDPOINTS**

Safety will be assessed by the following: monitoring and recording of AEs, clinical laboratory test results (hematology, serum chemistry, and urinalysis), vital sign measurements, 12-lead ECG results, and physical examination findings.

For all safety assessments, the investigator will determine whether results are clinically significant, which is defined as any variation in a result that has medical relevance or may result in an alteration in medical care (eg, active observation, diagnostic measures, or therapeutic measures). If clinical significance is noted, the result and reason for significance will be documented and an AE reported on the AE page of the participant's eCRF. The investigator will monitor the participant until the result has reached the reference range or the result at screening, or until the investigator determines that follow-up is no longer medically necessary.

### **6.2.1 Sponsor Communication**

The sponsor Medical Monitor will be contacted as quickly as possible for Grade 2 or above changes in blood AST, ALT, GGT, bilirubin (total or fractionated), or creatinine, or  $\geq$  Grade 3 laboratory abnormalities or adverse events. Communication with the sponsor Medical Monitor should not delay immediate management of the participant.

## 6.2.2 Adverse Events

Adverse events will be assessed from the time the participant signs the ICF until EOS and should be followed until they are resolved, stable, or judged by the investigator to be not clinically significant.

The investigator is responsible for ensuring that all AEs and SAEs are recorded in the eCRF and reported to the sponsor, regardless of their relationship to study drug or clinical significance. If there is any doubt as to whether a clinical observation is an AE, the event should be reported.

### 6.2.2.1 Adverse Event Definitions

An AE is defined as any untoward medical occurrence associated with the use of a drug in humans, whether or not considered drug related. Participants will be instructed to contact the investigator at any time after randomization if any symptoms develop.

A TEAE is defined as any event not present before exposure to study drug or any event already present that worsens in intensity or frequency after exposure. TEAE will be assessed from first dose of study drug until EOS and should be followed until they are resolved, stable, or judged by the investigator to be not clinically significant.

A suspected adverse reaction is any AE for which there is a reasonable possibility that the study drug caused the AE. For the purposes of investigational new drug safety reporting, “reasonable possibility” means that there is evidence to suggest a causal relationship between the study drug and the AE. A suspected adverse reaction implies a lesser degree of certainty about causality than an adverse reaction.

An AE or suspected adverse reaction is considered “unexpected” if it is not listed in the investigator brochure or if it occurs with specificity or severity that has not been previously observed with the study drug being tested; or, if an investigator brochure is not required or available, the AE or suspected adverse reaction is not consistent with the risk information described in the general investigational plan or elsewhere in the current application. For example, under this definition, hepatic necrosis would be unexpected (by virtue of greater severity) if the investigator brochure referred only to elevated hepatic enzymes or hepatitis. Similarly, cerebral thromboembolism and cerebral vasculitis would be unexpected (by virtue of greater specificity) if the investigator brochure listed only cerebral vascular accidents. “Unexpected,” as used in this definition, also refers to AEs or suspected adverse reactions that are mentioned in the investigator brochure as occurring with a class of drugs or as anticipated from the pharmacological properties of the drug but are not specifically mentioned as occurring with the particular drug under investigation.

An AE is considered an SAE/suspected unexpected serious adverse reaction if, in the view of either the investigator or sponsor, it results in any of the following outcomes:

- Death
- Life-threatening AE

- Inpatient hospitalization or prolongation of existing hospitalization
- Persistent or significant incapacity or substantial disruption of the ability to conduct normal life functions
- Congenital anomaly or birth defect

Important medical events that may not result in death, be life threatening, or require hospitalization may be considered serious when, based upon appropriate medical judgment, they may jeopardize the participant and may require medical or surgical intervention to prevent one of the outcomes listed in this definition. Examples of such medical events include allergic bronchospasm requiring intensive treatment in an emergency room or at home, blood dyscrasias or convulsions that do not result in inpatient hospitalization, or the development of drug dependency or drug abuse.

An AE or suspected adverse reaction is considered “life threatening” if, in the view of either the investigator or sponsor, its occurrence places the participant at immediate risk of death. It does not include an AE or suspected adverse reaction that might have caused death if it had been more severe.

#### **6.2.2.2 Eliciting and Documenting Adverse Events**

Participants will be asked a standard question to elicit any medically related changes in their well-being. They will also be asked if they have been hospitalized, had any accidents, used any new medications, or changed concomitant medication regimens (both prescription and over-the-counter medications).

In addition to participant’s observations, AEs will be documented from any data collected on the AE page of the eCRF (eg, laboratory values, physical examination findings, and ECG changes) or other documents that are relevant to participant safety.

#### **6.2.2.3 Reporting Adverse Events**

All AEs reported or observed during the study will be recorded on the AE page of the eCRF. Information to be collected includes drug treatment, type of event, time of onset, dosage, investigator-specified assessment of severity, seriousness, and relationship to study drug, time of resolution of the event, seriousness, any required treatment or evaluations, and outcome. Any AEs resulting from concurrent illnesses, reactions to concurrent illnesses, reactions to concurrent medications, or progression of disease states must also be reported. All AEs will be followed until they are resolved, stable, or judged by the investigator to be not clinically significant. The Medical Dictionary of Regulatory Activities will be used to code all AEs.

Any medical condition that is present at the time that the participant is screened but does not deteriorate should not be reported as an AE. However, if it deteriorates at any time during the study, it should be recorded as an AE.

Any AE that is considered serious by the investigator or which meets SAE criteria (Section 6.2.2.1) must be reported to the sponsor immediately (after the investigator has confirmed the occurrence of the SAE). The investigator will assess whether there is a reasonable possibility that the study drug caused the SAE. The sponsor will be responsible for notifying the relevant regulatory authorities of any SAE as outlined in US Title 21 CFR Parts 312 and 320. The investigator is responsible for notifying the IRB directly.

For this study, the following contact information will be used for SAE reporting:

ICON Drug Safety  
[contact]  
[contact]

#### **6.2.2.4 Assessment of Severity**

Seriousness (Section 6.2.2.1) and severity of an event are not synonymous. The severity (or intensity) of an AE refers to the extent to which it affects the participant's daily activities and will be classified as mild, moderate, or severe using the following criteria:

- Mild: These events require minimal or no treatment and do not interfere with the participant's daily activities.
- Moderate: These events result in a low level of inconvenience or require minor therapeutic measures. Moderate events may cause some interference with normal functioning.
- Severe: These events interrupt a participant's usual daily activity and may require systemic drug therapy or other treatment. Severe events are usually incapacitating.

Changes in the severity of an AE should be documented to allow the duration of the event at each level of intensity to be assessed. An AE characterized as intermittent does not require documentation of the onset and duration of each episode.

The Common Toxicity Criteria for Adverse Events (CTCAE) V5.0 grading criteria will also be used for assessment of severity of AEs.

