### **7.2 ANALYSIS SETS**

The analysis populations are as follows:

- The PK population will include participants who receive at least 1 dose of plixorafenib with or without cobicistat and have sufficient concentration data to support accurate estimation of at least 1 PK parameter. Participants who experience vomiting within 2 times the median  $T_{\max}$  after study drug dosing will be excluded from the PK analysis.
- The safety population will include all participants who receive at least 1 dose plixorafenib with or without cobicistat.

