4.3. Analysis Sets

Part A and Part B

The safety set will include all participants who received at least 1 dose of plixorafenib.

The PK population will include participants who receive at least 1 dose of plixorafenib and have sufficient concentration data to support accurate estimation of at least 1 PK parameter. Participants who experience vomiting within 2 times the median T_{max} after study drug dosing will be excluded from the PK analysis.

For Part A, all enrolled participants may be used for analysis. This set will include all participants who, according to the study investigator on the electronic case report form (eCRF), had met all eligibility criteria and were ready for randomization, regardless of whether they were then randomized or not.

5. Participant Disposition

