All AEs will be coded using MedDRA (version to be delineated in the CSR). The TEAEs will also be summarized, by treatment and overall population, by system organ class (SOC), preferred term (PT), by CTCAE toxicity grade, and either:

- Part A: by Relationship to study treatment.
- Part B: or for related TEAEs only.

Treatment Emergent AESIs will also be presented by SOC and PT, by treatment and overall.

An additional table will summarize the TEAEs by treatment sequence and overall, by SOC and PT.

The TEAE summary tables will be sorted by SOC and PT. System organ class will be displayed alphabetically. Preferred term will be displayed in descending order of overall frequency and then alphabetically within SOC. A participant with 2 or more events within the same level of summarization will be counted only once in that level using the highest CTCAE grade, or most related incident (for Part A summary by relationship only). Percentages will be based on the number of participants in the safety set.

All AEs will be presented in a data listing. Separate data listings will be generated for treatment related AEs, AESIs, SAEs, and AEs leading to treatment discontinuation.

For Part A and B, a TEAE will be assigned to the last treatment received prior to the assessment/observation as below:

- Treatment received in Treatment Period 1 if the AE start date/time is on or after the first dose of study drug in the Treatment Period 1, but prior to the first dose of study drug in Treatment Period 2.
- Treatment received in Treatment Period 2 if the AE start date/time is on or after the first dose of study drug in the Treatment Period 2, but prior to the first dose of study drug in Treatment Period 3.
- Treatment received in Treatment Period 3 if the AE start date/time is on or after the first dose of study drug in the Treatment Period 3.

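### The Protocol lets one intermittent adverse event record run across later doses, while the SAP assigns events to treatments by start time alone, so incidence on the later treatments can be under-counted

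*Protocol*

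**What the plan says.** Protocol 6.2.2.3 sets the general content of an adverse event record: "Information to be collected includes drug treatment, type of event, time of onset, dosage, investigator-specified assessment of severity, seriousness, and relationship to study drug", with time of resolution also listed. Protocol 6.2.2.4 then relaxes this for one class of event: "An AE characterized as intermittent does not require documentation of the onset and duration of each episode". The sentence before it keeps one safeguard: "Changes in the severity of an AE should be documented to allow the duration of the event at each level of intensity to be assessed".

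SAP 8.1 sets the attribution rule: "a TEAE will be assigned to the last treatment received prior to the assessment/observation as below". Three windows follow, one per treatment period. The Period 2 condition, for instance, reads "if the AE start date/time is on or after the first dose of study drug in the Treatment Period 2, but prior to the first", with the Period 3 dosing as its upper limit. Start date and time is the only variable used.

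A second rule also depends on time after a dose. Protocol 7.2 provides that "Participants who experience vomiting within 2 times the median" Tmax after dosing are left out of the PK analysis, and SAP 4.3 repeats it. Neither section says where the time of vomiting is recorded. SAP 4 leaves PK data handling to a separate sponsor document.

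**The concern.** Each participant receives three single doses seven days apart, each under a different condition. Symptoms such as headache or nausea may come back after more than one dose. The attribution rule can place a recurrence on the right treatment only if that recurrence has its own start time, and Protocol 6.2.2.4 tells the site that such a time need not be recorded once the event is called intermittent.

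At stake is the by-treatment adverse event tabulation. Safety with and without cobicistat is among the primary objectives of both parts, and SAP 8.1 reports events by treatment. The gap lies in data capture, so a later change to the SAP rule cannot recover onset times that the site was not required to record.

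**Working it through.** The plan states no figure on this point, so there is nothing to reproduce. The check compares the rules and then works out what one affected record does.

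**1. Does any rule close the gap?**
- Protocol 6.2.2.3 collects an onset time per record. Protocol 6.2.2.4 is the more specific rule and waives it per episode.
- The severity-change rule in 6.2.2.4 dates a change in intensity. A recurrence at the same severity produces no dated entry.
- The definition of a treatment-emergent event (Protocol 6.2.2.1, SAP 8.1) covers worsening in frequency, but it does not date a recurrence at unchanged severity and frequency.
- Nothing supplied limits the waiver to one period or requires a new record when an event returns after a later dose.

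**2. Recipients per treatment at full enrolment** (Protocol 3.1 and 3.2; SAP Tables 3-2 and 3-4)
- Part A: 12 participants, all receiving all three treatments, so 12 per treatment.
- Part B: 16 participants over 4 sequences, so 4 per sequence. Each treatment appears in 3 of the 4 sequences: 3 × 4 = 12 per treatment.

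**3. Effect of one affected participant on one treatment's incidence**
- Denominator of recipients: 1/12 = 8.3 percentage points, in either part.
- Part B with the whole safety set as denominator, which is the literal reading of the percentage rule in SAP 8.1: 1/16 = 6.25 points.

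**4. Opportunities.** Every dose after the first is a chance for a recurrence to be absorbed into an earlier record: 12 × 2 = 24 dosings in Part A and 16 × 2 = 32 in Part B. The documents do not give the share that would be affected.

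**5. Illustration (assumed).** Take one participant per sequence with a symptom that starts in Period 1 and returns after both later doses. A single record is credited to the Period 1 treatment only; separate records are credited to all three treatments received.

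| | Participants counted per treatment, single record | Participants counted per treatment, dated episodes |
|---|---|---|
| Part A (6 sequences) | 2 | 6 |
| Part B (4 sequences) | 1 | 3 |

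The shortfall is the same for every treatment, because each comes first in 2 of the 6 Part A sequences and in 1 of the 4 Part B sequences.

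**The case against.** The waiver permits omission and does not require it. Under Protocol 6.2.2.3, a headache that resolves on Day 1 and returns after the Day 8 dose can naturally be entered as a resolved event and then a new one, each with its own treatment and onset. Causality is judged partly on timing after administration (Protocol 6.2.2.5), which also fits poorly with one record spanning different regimens. The eCRF completion instructions were not supplied and may already split records by period. All of this stands. It means that recurrences can be missed, not that they will be. Episodes confined to one period are assigned correctly in any case.

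A reader might infer more than the documents support:
- **That events are tilted toward whichever treatment came first.** The Period 1 event is correctly placed and its incidence is not inflated. First-period treatments are balanced by design, so the expected effect is a shortfall spread over the treatments. A chance imbalance among a few participants is possible.
- **That two-thirds of occurrences are lost.** This is true only of a participant with the symptom after all three doses, recorded once.
- **That PK ratios are biased by undetected vomiting.** The vomiting rule needs a time after each dose, but neither document says that the time comes from the adverse event onset field, and the PK plan was not supplied. The rule also excludes participants, not single-period profiles. Bias in the food or cobicistat comparisons is therefore only a possibility.

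**Conclusion.** The conflict between Protocol 6.2.2.4 and SAP 8.1 is real and should be removed. An intermittent record that spans a later dose is credited only to the treatment at first onset, so the later treatment is under-counted by 8.3 points per affected participant, or 6.25 points in Part B on a denominator of 16. This rests on full enrolment and on a site choosing to merge episodes across periods; the frequency of that is unknown. The adverse event analysis is descriptive, and sample size, alpha and power are untouched. The change is worth making because it costs little, serves a primary objective and cannot be made good at the analysis stage. SAP 11 already adds a laboratory summary to guard against cross-period masking, and adverse events have no equivalent.

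**What to change.** Amend Protocol 6.2.2.4 along these lines, and mirror it in the eCRF completion instructions:

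- The waiver of episode-level onset and duration applies only to episodes within one treatment period.
- An episode that starts after a later dose is entered as a new adverse event with its own onset date and time.
- The clock time of any vomiting on Days 1, 8 and 15 is recorded, unless it is already captured elsewhere.

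The attribution rule in SAP 8.1 can then stand. Apply the change prospectively to Part B. Part A had been analysed before Part B was designed (SAP 10), so new wording cannot restore its data. There, check intermittent records that span a later dose against source documents and report how many cannot be resolved.

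The cost is wording in two documents and a few more adverse event lines. Participants are confined from Day -1 to Day 19, so episodes can be observed and timed. The raw event count in the overall summary of SAP 8.1 will rise, while counting each participant once per level limits the effect on incidence to recurrences that were previously missed. Any exploratory summary pooling the two parts (SAP 4) should note that they may have been recorded under different conventions.
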